5.1. Overall Design

This will be a single-dose, subject-blind, 3-period, 3-treatment, randomized, crossover study in healthy subjects.

All subjects will be screened within 28 days prior to enrollment. Eligible subjects will be admitted to the clinical research unit (CRU) on Day -1 and randomized 1:1:1 to 1 of 3 possible treatment sequences (see Figure RHCS.1). On Day 1, subjects will receive a single 1-mL SC injection of 1 of the following treatments, according to the randomization schedule:

- 80 mg ixekizumab Commercial Formulation (Reference)
- 80 mg ixekizumab Test Formulation 1
- 80 mg ixekizumab Test Formulation 2

Subjects may be allowed to leave the CRU after completing the 4-hour safety assessments for Day 1, at the investigator's discretion. Subjects will be readmitted to the CRU on Days 7 and 14 to receive their second and third injections on Days 8 and 15, respectively, and may be allowed to leave the CRU after completing the 4-hour safety assessments at the investigators discretion on Days 8 and 15, respectively. Subjects will return to the CRU as an outpatient on Days 21 (\pm 1 day) and 43 (\pm 3 days) for a safety check-up. In addition, safety follow-up telephone calls will be conducted in between outpatient visits, on Days 28 (\pm 1 day), 35 (\pm 3 days), 50 (\pm 3 days), 57 (\pm 3 days), and 64 (\pm 3 days), with a final safety follow-up telephone call on Day 71 (\pm 3 days). There will be a follow-up visit approximately 12 weeks after the last injection.

Site staff will administer all injections. All injections will be administered in the abdomen while the subject is in a sitting or a reclining position. Subsequent injections will be alternated between the abdominal quadrants. The injection site will be documented. Injections should not be made into an area that shows evidence of bruising, redness, or a rash from a previous injection. All study injection sites will be marked for size and with a surgical marker in order to identify study injection sites. Every attempt will be made to have injections for individual subjects be performed by the same clinical staff member.

[figure not shown]
Injection-site assessments will be administered immediately after each injection and at 10, 20, 30, 60, 120, and 240 minutes post injection. The injection-site pain VAS will be administered immediately after each injection and at 10, 20, 30, and 60 minutes post-injection.

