10.3.1.2. Statistical Evaluation of Safety

10.3.1.2.1. Injection-Site Pain

VAS pain score will be summarized using standard descriptive statistics. In addition, the severity of pain will be categorized by VAS pain score as: mild pain (\leq 30), moderate pain (\geq 30 and \leq 70), and severe pain (\geq 70). The number and percentage of the subjects in each pain severity category will be summarized by treatment and time point.

A mixed-effects repeated measures analysis model will be used to analyze the continuous injection-site pain VAS score by each time post-injection (0, 10, 20, 30, and 60 minutes). For measures at each time post-injection, the model will include treatment, period (Day 1, Day 8, or Day 15), treatment sequence, and treatment by treatment sequence as fixed effects. The covariance structure of the model will be unstructured. The Kenward-Roger method will be used to estimate the denominator degrees of freedom. Type III sums of squares for the least squares means will be used for the statistical comparison; treatment differences on every time point will be reported, along with the corresponding 95% confidence intervals for the differences. All pair-wise treatment comparisons by measuring time point will be evaluated and presented.

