Appendix 6. Protocol Amendment I1F-MC-RHCS (b)
Summary: A Randomized Study to Investigate
Injection-Site Pain Following Subcutaneous Injections of
2 Ixekizumab Test Formulations Compared to the
Commercial Formulation using a Pre-filled Syringe in
Healthy Subjects

Overview

Protocol I1F-MC-RHCS, A Randomized Study to Investigate Injection-Site Pain Following Subcutaneous Injections of 2 Ixekizumab Test Formulations Compared to the Commercial Formulation using a Pre-filled Syringe in Healthy Subjects, has been amended. The new protocol is indicated by Amendment (b) and will be used to conduct the study in place of any preceding version of the protocol.

Temperature assessments were added to each site visit. In addition, weekly safety telephone calls were added in between outpatient visits as appropriate.

The additional study activities were implemented to further monitor the health of subjects due to emerging data in response to a reporting of an SAE in the I1F-MC-RHCT study.

Enrollment into this study was paused in April 2019 to evaluate a potential safety concern observed in the I1F-MC-RHCT (PK Study). Approximately 80% of the VAS data had been collected; the team decided to conduct the protocol specified interim analysis based on all the available data, and stop enrolling new subjects.

Revised Protocol Sections

Note: All deletions have been identified by strikethroughs.

All additions have been identified by the use of underscore.

1. Protocol Synopsis

Subjects may be allowed to leave the CRU after completing the 4-hour safety assessments for Day 1, at the investigator's discretion. Subjects will be readmitted to the CRU on Days 7 and 14 to receive their second and third injections on Days 8 and 15, respectively, and may be allowed to leave the CRU after completing the 4-hour safety assessments at the investigators discretion on Days 8 and 15, respectively. Subjects will return to the CRU as an outpatient on Days 21 (± 1 day) and 43 (± 3 days) for a safety check-up. In addition, A safety follow-up telephone calls will be conducted in between outpatient visits, on Days 28 (± 1 day), 35 (± 3 days), 50 (± 3 days), ± 57 (± 3 days), and 64 (± 3 days), with a final safety follow-up telephone call on Day 71 (± 3 days). There will be a follow-up visit approximately 12 weeks after the last injection.

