#### 5. STUDY DESIGN

This will be a single-dose, subject-blind, 3-period, 3-formulation, randomized, crossover study in healthy subjects.

All subjects will be screened within 28 days prior to enrollment. Eligible subjects will be admitted to the clinical research unit (CRU) on Day -1 and randomized 1:1:1 to 1 of 3 possible

[figure not shown]
Final, 8 January 2019 Page 4 of 10

formulation sequences (see Figure 1). On Day 1, subjects will receive a single 1-mL SC injection of 1 of the following formulations, according to the randomization schedule:

- 80 mg ixekizumab Commercial Formulation (Reference)
- 80 mg ixekizumab Test Formulation 1
- 80 mg ixekizumab Test Formulation 2

Subjects may be allowed to leave the CRU after completing the 4-hour safety assessments for Day 1, at the investigator's discretion. Subjects will be readmitted to the CRU on Days 7 and 14 to receive their second and third injections on Days 8 and 15, respectively, and may be allowed to leave the CRU after completing the 4-hour safety assessments at the investigator's discretion on Days 8 and 15, respectively. Subjects will return to the CRU as an outpatient on Days 21 ( $\pm$  1 day) and 43 ( $\pm$  3 days) for a safety check-up. A safety follow-up telephone call will be conducted on Day 71 ( $\pm$  3 days). There will be a follow-up visit approximately 12 weeks after the last injection.

#### Group 1

Subjects will be blinded to all treatments.

Figure 1. Illustration of study design.

Final, 8 January 2019 Page 5 of 10

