#### 7. SAMPLE SIZE JUSTIFICATION

Up to 102 subjects may be enrolled to maximize the intent to have 78 subjects (26 subjects per formulation sequence) complete the study.

The objective of this study is to evaluate the injection pain immediately following dosing.

Because of the crossover study design, each subject will have the opportunity to receive each formulation.

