#### 9.3.10 Injection Site Pain Assessment

Pain measurements will be quantified using the 100-mm VAS pain score (100-mm line anchored by verbal descriptors, usually "no pain" and "worst imaginable pain) for all subjects, whether or not they report injection pain.

Final, 8 January 2019 Page 8 of 10

VAS pain score will be summarized using standard descriptive statistics. In addition, the severity of pain will be categorized by VAS pain score as: mild pain ( $\leq$ 30), moderate pain ( $\geq$ 30 and  $\leq$ 70), and severe pain ( $\geq$ 70). The number and percentage of the subjects in each pain severity category will be summarized by formulation and time point. Figures of the continuous injection-site pain VAS score will also be presented, by formulation and measuring time point.

A mixed-effects repeated measures analysis model will be used to analyze the continuous injection-site pain VAS score by each time post-injection (0, 10, 20, 30, and 60 minutes). For measures at each time post-injection, the model will include formulation, period (Day 1, Day 8, or Day 15), formulation sequence, and formulation by formulation sequence as fixed effects. The covariance structure of the model will be unstructured. The Kenward-Roger method will be used to estimate the denominator degrees of freedom. Type III sums of squares for the least squares means will be used for the statistical comparison; formulation differences on every time point will be reported, along with the corresponding 95% confidence intervals for the differences. All pair-wise formulation comparisons by measuring time point will be evaluated and presented.

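### With formulation-by-sequence in the primary VAS model, period has 0 Type III degrees of freedom and cannot be estimated; delete the interaction.

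*SAP*

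**What the plan says.** SAP 9.3.10 analyses the VAS score at each post-injection time with a mixed model in which "the model will include formulation, period (Day 1, Day 8, or Day 15), formulation sequence, and formulation by formulation sequence as fixed effects". Covariance is unstructured, degrees of freedom are Kenward-Roger, tests are Type III, and the reported results are pairwise formulation differences with 95% confidence intervals. Protocol section 10.3.1.2.1 has the same list with treatment in place of formulation: "the model will include treatment, period (Day 1, Day 8, or Day 15), treatment sequence, and treatment by treatment sequence as fixed effects". SAP section 12 records no departure from the protocol analysis.

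The design is a "single-dose, subject-blind, 3-period, 3-formulation, randomized, crossover study in healthy subjects" (SAP section 5). Subjects are "randomized 1:1:1 to 1 of 3 possible treatment sequences" (protocol 5.1). SAP section 7 plans for "78 subjects (26 subjects per formulation sequence) complete the study" and notes that "each subject will have the opportunity to receive each formulation". Neither document says what the interaction is for, or that period is determined by sequence and formulation together.

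**The concern.** Within a sequence, each formulation is given in exactly one period. Once the model has a separate mean for every formulation-sequence combination, nothing is left for period to explain. The authors name the three dosing days explicitly, so they evidently meant to adjust for period as a term. As written, that term is empty, and a real period effect, such as habituation to repeated injections, would appear as part of the interaction.

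This is the only inferential model for the primary endpoint, the VAS score within 1 minute of injection. Three things are at stake:

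- whether the formulation differences can still be estimated;
- whether they lose precision;
- whether an interaction result could be misread as formulations behaving differently by sequence.

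**Working it through.** **Inputs.** Three periods, 3 formulations and 3 sequences, with each formulation scheduled once per subject (SAP sections 5 and 7, protocol 5.1). The four fixed effects come from SAP 9.3.10, and 26 completers per sequence from SAP section 7 (3 × 26 = 78, consistent). The documents give no degrees of freedom, SD or correlation for this model, so there is no stated figure to reproduce. The SDs, correlations and any counts other than 26 below are assumptions. The order of formulations in each sequence is in a figure not available to this review.

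**1. Rank.** There are 3 × 3 = 9 sequence-by-period cells, so the mean model can have rank at most 9.

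| Terms (plus intercept) | Rank |
|---|---|
| formulation + period + sequence | 1 + 2 + 2 + 2 = 7 |
| formulation + sequence + formulation × sequence | 1 + 2 + 2 + 4 = 9 |
| all four terms (19 columns) | 9 |

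Type III df for period = 9 − 9 = 0. Type III df for the interaction = 9 − 7 = 2, not its nominal 4; the other 2 are the period effect.

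**2. Dependence on the unseen figure.** Three sequences can be chosen from the 6 possible orders in 20 ways.

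- Period differences are estimable in 0 of the 20.
- Formulation LS-mean differences under the planned model are estimable in the 2 sets that form Latin squares, and in none of the other 18.
- The additive model estimates all three formulation differences in all 20.

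**3. Precision, Latin square, additive model true, covariance treated as known.** Under the planned model, a formulation difference is the simple average of three within-sequence differences. In a cyclic square each pair of periods is used once, so at n per sequence:

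Var = [(σ₁² + σ₂² − 2rσ₁σ₂) + (σ₂² + σ₃² − 2rσ₂σ₃) + (σ₁² + σ₃² − 2rσ₁σ₃)] / (9n)

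With n = 26 (9n = 234) and r = 0.5:

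| Assumed period SDs | Planned variance | Planned SE | Additive SE (GLS) | Ratio |
|---|---|---|---|---|
| 22/22/22 | (484 + 484 + 484)/234 = 6.205 | 2.491 | 2.491 | 1.000 |
| 25/22/20 | (559 + 444 + 525)/234 = 6.530 | 2.555 | 2.532 | 1.009 |
| 28/22/18 | (652 + 412 + 604)/234 = 7.128 | 2.670 | 2.575 | 1.037 |

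For SDs 28/22/18 the ratio is 1.035 to 1.043 over r = 0.3 to 0.7.

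These rows share one correlation across periods. If the correlations also differ, the loss can be larger. With variances 1.3/1.0/0.8 and correlations of 0.35 (periods 1 and 2), 0.49 (1 and 3) and 0.78 (2 and 3), the planned SE is √[(1.5 + 0.4 + 1.1)/234] = 0.113. The additive SE is 0.087, a ratio of about 1.31.

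**4. After enrolment stopped.** Protocol Appendix 6 reports "Approximately 80% of the VAS data had been collected". If that means about 0.8 × 78 ≈ 62 completers, split 21/21/20, the ratio is 1.0001 with equal covariance and 1.032 to 1.040 with SDs 28/22/18 and r = 0.5. With unequal sequence sizes or unequal covariance the point estimates of the two models also differ, because the planned model averages the sequences equally and the additive model weights them.

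**5. Is the interaction a carry-over test?** In a 3-sequence cyclic square, formulation + period + sequence + previous formulation also has rank 9, and combining it with the planned model still gives 9. The two span the same space. The 2 remaining df therefore cannot distinguish carry-over from sequence-specific formulation effects. Adding the previous-formulation term raises the SE of a formulation difference to 2.236 times the additive SE (26 per sequence, equal covariance).

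**The case against.** The strongest reply accepts the algebra and disputes its consequence. The model can be run: period is redundant and does not block estimation. The planned outputs are formulation differences and intervals, and no period estimate or test is promised. Three sequences allocated 1:1:1 to three formulations in three periods look like a Latin square, in which those differences remain estimable and a pure period effect gives no bias. At 26 per sequence with equal covariance nothing changes numerically, and any larger cost rests on assumed covariances. Dropping period instead would give the identical fit. The study is described as exploratory, with no power calculation or success rule. A change made after VAS data have been seen by treatment is also more than an edit.

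Most of this stands as a limit on severity. The primary comparison survives under a Latin square, and the sets of sequences that would break it are probably excluded by the figure. The size of the precision loss is not known.

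It does not justify keeping the model. The plan names an adjustment that it cannot make. Dropping period would leave a saturated model with the period effect hidden in the interaction. The interaction serves no stated purpose, and its 2 usable df cannot isolate carry-over. Having to date and report the change is an obligation, not a large cost.

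**Conclusion.** The concern holds. The 0 df for period is exact for subjects dosed as randomised and does not depend on which three sequences were used. It is a Type III result, which is the type the plan specifies; a sequential test with period entered before the interaction would show 2 df. Dosing out of order, analysed as received, could break the aliasing for a few subjects, but the plan cannot rely on that.

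The primary comparison is not invalidated, provided the sequences form a Latin square. If the additive model is true and the covariance known, deleting the interaction never worsens precision. The gain ranges from nothing (equal covariance, equal sequences) through about 1% to 4% of the SE (unequal SDs, common correlation) to about 31% in the one covariance tried with unequal correlations. These are illustrations, not predictions. The correction should be made, but it does not threaten the trial's main result.

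**What to change.** Delete the formulation-by-sequence term from SAP 9.3.10 and the treatment-by-sequence term from protocol 10.3.1.2.1. The fixed effects become formulation, period and sequence; keep the unstructured covariance across periods and the Kenward-Roger degrees of freedom. Period then has 2 df, and all three formulation differences are estimable for any set of three sequences.

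If a carry-over check is wanted, specify it as a separate, labelled sensitivity analysis that does not replace the primary estimate, and state that it saturates the mean model in a 3-sequence cyclic square and at least doubles the standard error (2.236 times under equal covariance).

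The cost is one phrase in each document, with no change to data collection or sample size. Date and justify the change relative to the interim analysis, which includes VAS data, and report it in the clinical study report as protocol 10.3 and SAP section 3 require. If only the SAP is changed, section 12 needs an entry too.

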#### 10. DATA REVIEW DURING THE STUDY

Data will be reviewed by the investigator throughout the course of the study to ensure subject safety.

#### 11. INTERIM ANALYSES

One formal interim analysis is planned for this study. The interim analysis will include review of all subjects' safety data (AEs, VAS and injection site reaction [ISR] data) collected up to and including Day 21.

# 12. CHANGES FROM THE PROTOCOL SPECIFIED STATISTICAL ANALYSES

There were no changes from the protocol specified statistical analyses.

#### 14. DATA PRESENTATION

#### 14.1 Derived Parameters

Individual derived parameters and appropriate summary statistics will be reported to three significant figures. N and percentage values should be reported as whole numbers. Median values should be treated as an observed parameter and reported to the same number of decimal places as minimum and maximum values.

#### 14.2 Missing Data

Missing data will not be displayed in listings.

#### 14.3 Insufficient Data for Presentation

Some of the TFLs may not have sufficient numbers of subjects or data for presentation. If this occurs, the blank TFL shell will be presented with a message printed in the centre of the table, such as, "No serious adverse events occurred for this study."

Final, 8 January 2019 Page 10 of 10
